2.4.7.1 Study methodology endpoints: Patient satisfaction with trial experience (WIWI)

Descriptive statistics (mean, median, SD, minimum and maximum) for each score will be presented by study conduct approach group at Week 24.

WIWI scores (1 score for each item) will be compared between approach groups using an ANOVA. This model will include fixed categorical effects of study conduct approach group, of randomization strata of screening HbA1c (<7.6%, ≥7.6%) and randomization strata of sites.

2.4.7.2 Study methodology endpoints: Impact of trial participation patient reported outcome (WPAI-SP)

Descriptive statistics (mean, median, SD, minimum and maximum) for each score and combined scores will be presented by study conduct approach group at baseline and Week 24.

The change in WPAI-SP scores from baseline to Week 24 will be analyzed using an ANCOVA. This model will include fixed categorical effects of study conduct approach group, on randomization strata of screening HbA1c (<7.6%, ≥7.6%) and randomization strata of sites as well as continuous fixed covariates of corresponding baseline score.

2.4.7.3 Study methodology endpoints: Patient burden with trial participation (OSEP)

Descriptive statistics (mean, median, SD, minimum and maximum) for each score and combined scores will be presented by study conduct approach group at baseline (OSEP (Part 1)) and Week 24 (OSEP (Part 1), OSEP (Part 2)).

The change in OSEP (Part 1) score from baseline to Week 24 will be analyzed using an ANCOVA. This model will include fixed categorical effects of study conduct approach group, on randomization strata of screening HbA1c (<7.6%, ≥7.6%) and randomization strata of sites as well as continuous fixed covariates of corresponding baseline score.

OSEP (Part 2) score will be compared between study conduct approach groups using an ANOVA. This model will include fixed categorical effects of study conduct approach group, on randomization strata of screening HbA1c (<7.6%, ≥7.6%) and randomization strata of sites.

2.4.7.4 Study methodology endpoints: Resource use (RUQ)

Descriptive summary (mean, median, SD, minimum and maximum) will be provided for each study conduct approach group at baseline and for each applicable on-treatment visit on the following items:

- Total number of visits (overall and per healthcare professional type)
- Total money spent
- Total time spent

In addition, the total and average resource utilization per patient will be calculated on all on-treatment questionnaires. The change between baseline and this on-treatment average will be calculated.

A plot will be provided for each 3 above items.

2.4.7.5 Diabetes control endpoints: Diabetes-related patient reported outcomes (DTSQs, DTSQc, HFS-II, DDS)

For each PRO questionnaire total and domain scores:

A graphical presentation will be used to illustrate trends over time per study conduct approach group, by visit on mean scores $\pm\sqrt{2}$ SE and on change from baseline values $\pm\sqrt{2}$ SE.

Cumulative distribution functions of PRO changes from baseline to Week 24 will be plotted by study conduct approach group.

The Diabetes Treatment Satisfaction Questionnaire Status Version (DTSQs)

Descriptive summary (mean, median, SD, minimum and maximum) at each visit (baseline and Week 24) and change from baseline to Week 24 will be provided including:

- “total treatment satisfaction” score (sum of items 1, 4, 5, 6, 7 and 8), score ranging is from 0 (no satisfaction) to 36 (high satisfaction with treatment).
- “perceived frequency of hyperglycemia” score (Item 2), score ranging is from 0 (none of the time) to 6 (most of the time).
- “perceived frequency of hypoglycemia” score (Item 3), score ranging is from 0 (none of the time) to 6 (most of the time).

The change for each DTSQs scores from baseline to Week 24 will be analyzed using an ANCOVA. This model will include fixed categorical effects of study conduct approach group, randomization strata of screening HbA1c (<7.6%, \geq 7.6%) and randomization strata of sites as well as continuous fixed covariates of corresponding baseline score.

The change for each DTSQs scores from baseline to Week 24 will be analyzed using cumulative distribution functions of scores. Changes from baseline will be displayed by study conduct approach group, for each the 3 DTSQs scores and a graphical presentation will be used to illustrate trends over time per study conduct approach group by visit on mean scores $\pm\sqrt{2}$ SE and on change from baseline values $\pm\sqrt{2}$ SE.

The Diabetes Treatment Satisfaction Questionnaire Change Version (DTSQc)

Descriptive summary (mean, median, SD, minimum and maximum) at Week 24 will be provided including:

- “total treatment satisfaction” score (sum of items 1, 4, 5, 6, 7 and 8), score ranging is from -18 to 18. Positive scores are indicative of improvement in treatment satisfaction, whereas negative scores are indicative of deterioration in treatment satisfaction. A score of 0 represents no change.
- “perceived frequency of hyperglycemia” score (Item 2), score ranging is from -3 (‘much less of the time now’) to +3 (‘much more of the time now’), meaning negative scores indicate fewer problems with blood glucose levels and positive scores indicate more problems than before. A score of 0 represents no change.

- “perceived frequency of hypoglycemia” score (Item 3), score ranging is from -3 (‘much less of the time now’) to +3 (‘much more of the time now’), meaning negative scores indicate fewer problems with blood glucose levels and positive scores indicate more problems than before. A score of 0 represents no change.

Average scores at Week 24 in total treatment satisfaction score, hyperglycemia perception and hypoglycemia perception score from DTSQc will be analyzed using an ANCOVA model. This model will include fixed categorical effects of study conduct approach group, randomization strata of screening HbA1c (<7.6%, ≥7.6%), randomization strata of site, as well as continuous fixed covariates of corresponding baseline score from DTSQs.

Hypoglycemia Fear Survey-II (HFS-II)

Fear of hypoglycemia will be measured with the Hypoglycemia Fear Survey-II (HFS-II) at baseline and Week 24 (Visit 12). The HFS-II comprises 33 items:

- The hypoglycemia fear survey-behavior subscale [HFS-B] determined by computing the mean of the 15 items measuring behavior (score from 0 to 4).
- The hypoglycemia fear survey-worry subscale [HFS-W] determined by computing the mean of the 18 items measuring worry (score from 0 to 4).
- The total score determined by computing the mean of all 33 items (score from 0 to 4)

The change in HFS-II scores from baseline to Week 24 will be analyzed using an ANCOVA. This model will include fixed categorical effects of study conduct approach group, on randomization strata of screening HbA1c (<7.6%, ≥7.6%) and randomization strata of sites as well as continuous fixed covariates of corresponding baseline score.

Diabetes Distress Scale (DDS)

Descriptive summary (mean, median, SD, minimum and maximum) at each visit (baseline and Week 24) and change from baseline to Week 24 will be provided including the total score and the 4 domains scores determined by computing the mean of item responses:

- Emotional burden score: mean of items 2, 4, 7, 10 and 14 (score from 0 to 6).
- Physician distress score: mean of items 1, 5, 11 and 15 (score from 0 to 6).
- Regimen distress score: mean of items 6, 8, 3, 12 and 16 (score from 0 to 6).
- Interpersonal distress score: mean of items 9, 13 and 17 (score from 0 to 6).
- Total DDS score: mean of the 17 items (score from 0 to 6).

The change in DDS scores from baseline to Week 24 will be analyzed using an ANCOVA. This model will include fixed categorical effects of study conduct approach group, on randomization strata of screening HbA1c (<7.6%, ≥7.6%) and randomization strata of sites as well as continuous fixed covariates of corresponding baseline score.

The incidence of patients experiencing a score ≥ 3 (in DDS total score and domain scores) as well as responder patients (in DDS total score and domain scores) will be determined, during the 24-week randomized period.

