Diabetes-related distress will be measured using the Diabetes Distress Scale (DDS) (16) at Week 0 (Visit 2-Step 2) and Week 24 (Visit 12). The DDS contains 17 items related to potential problem areas that people with diabetes may experience. Patients are asked to consider the degree to which each of the items may have distressed or bothered them during the past month, and respond between 1 (not a problem) and 6 (a very serious problem). The DDS yields a total diabetes distress score and 4 subscale scores, each addressing a different kind of distress (emotional burden, physician distress, regimen distress, interpersonal distress). Each score (total and subscales) are presented as an average, by summing the patient’s responses to the appropriate items and divide by the number of items in that scale. In addition, total and subscale scores will be categorized: a mean score 2.0 – 2.9 should be considered ‘moderate distress’ and a mean score >3.0 should be considered ‘high distress’ (17).

The DDS will be administered electronically using mobile technology.

See questionnaires in [Appendix C](#).

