11.4.3.2.1 Analysis of diabetes control PROs

For each questionnaire a descriptive summary at each applicable visit (baseline and/or Week 24) and change from baseline to Week 24 will be provided, including:

- DTSQs and DTSQc subscale scores (total treatment satisfaction, perceived frequency of hyperglycemia, and perceived frequency of hypoglycemia, see [Section 9.2.2.1](#))
- HFS-II total score and subscale scores (HFS-B and HFS-W)
- DDS: total score, subscales scores, distress category for total and subscales ([Section 9.2.2.1](#))

The change in DTSQs, HFS-II, and DDS scores from baseline to Week 24 will be analyzed using an ANCOVA. This model will include fixed categorical effects of approach group, on randomization strata of screening HbA1c (<7.6%, ≥7.6%) and randomization strata of sites as well as continuous fixed covariates of corresponding baseline score.

Average scores at Week 24 in total treatment satisfaction score, hyperglycemia perception, and hypoglycemia perception score from DTSQc will be analyzed using an ANCOVA model. This model will include fixed categorical effects of approach group, on randomization strata of screening HbA1c (<7.6%, ≥7.6%) and randomization strata of sites as well as continuous fixed covariates of corresponding baseline score from DTSQs.

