Higher total score reflects greater fear of hypoglycemia. A higher Behavior score reflects greater tendency to avoid hypoglycemia and/or its negative consequences. A higher Worry score reflects higher worry concerning episodes of hypoglycemia and its consequences.

See questionnaire in [Appendix I](#).

Diabetes Distress Scale (DDS)

Diabetes-related distress will be measured using the Diabetes Distress Scale (DDS) at baseline and Week 24 (Visit 12).

The DDS contains 17 items related to potential problem areas that people with diabetes may experience. Patients are asked to consider the degree to which each of the items may have distressed or bothered them during the past month, and respond between 1 (not a problem) and 6 (a very serious problem).

The DDS yields a total diabetes distress score and 4 subscale scores, each addressing a different kind of distress (emotional burden, physician distress, regimen distress, interpersonal distress).

Each score (total and subscales) are presented as an average, by summing the patient's responses to the appropriate items and divide by the number of items in that scale.

In addition, total and subscale scores will be categorized: a mean score 2.0 – 2.9 should be considered 'moderate distress' and a mean score >3.0 should be considered 'high distress'.

See questionnaire in [Appendix J](#).

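### The DDS distress categories leave a mean of exactly 3.0 (and a total such as 50/17 = 2.94) unclassified, while the SAP's separate incidence count includes patients at 3.0

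*SAP*

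**What the plan says.** The categories are defined identically in both documents. For the moderate band, SAP 2.1.7.5 has "total and subscale scores will be categorized: a mean score 2.0 – 2.9 should be considered". For the upper band it sets a strict inequality: "a mean score >3.0 should be considered 'high distress". Protocol 9.2.2.1 uses the same strict inequality ("and a mean score >3.0 should be considered" high) and attributes the cut points to a cited publication on DDS cut points.

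The categories are a planned output. Protocol 11.4.3.2.1 lists, among the descriptive summaries, "DDS: total score, subscales scores, distress category for total and subscales".

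SAP 2.4.7.5 adds a count with an inclusive threshold: "The incidence of patients experiencing a score ≥ 3 (in DDS total score and domain scores").

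On score construction, patients "respond between 1 (not a problem) and 6 (a very serious problem"), and each score is a mean of items, for example "Total DDS score: mean of the 17 items (score from 0 to 6"). Neither document gives a rounding rule for DDS means. SAP 1.5 and 1.6 both declare no modification to the protocol's statistical section or to the plan.

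**The concern.** A set of categories should place every attainable score in exactly one class. Here the moderate band stops at 2.9 and the high band starts strictly above 3.0. Because the scores are means of a few integers, 3.0 is an attainable value on every scale.

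The incidence output uses the same number with the other inequality. A patient at exactly 3.0 is therefore in the numerator of one output and absent from both named bands of the other. A programmer would have to decide what to do with that patient without guidance, and a reader of the report could not reconcile the two outputs. What is at stake is the descriptive reporting of one secondary patient-reported outcome.

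**Working it through.** The plan states no expected DDS incidence, so there is no figure to reproduce. The check is which scores are attainable, what each rule does with them, and how many patients might be involved.

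**Inputs.** Items are integers 1 to 6 (SAP 2.1.7.5). The total has 17 items; the domains have 5 (emotional), 4 (physician), 5 (regimen) and 3 (interpersonal) (SAP 2.4.7.5). The minimum numbers answered are 12 for the total and 4, 3, 4 and 2 for the domains (SAP 2.5.2, Table 1). The bands are as above.

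**Step 1: scores with no category.** With k items answered and sum S, the mean S/k lies in the gap if 2.9k < S ≤ 3k. S = 3k always qualifies. S = 3k − 1 qualifies only if k > 10, and S = 3k − 2 only if k > 20. So the domains have one gap value and the total has two.

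| Items answered | Interval for S | Gap sums | Means |
|---|---|---|---|
| 17 (total, complete) | 49.3 < S ≤ 51 | 50, 51 | 2.941, 3.000 |
| 12 (total, minimum) | 34.8 < S ≤ 36 | 35, 36 | 2.917, 3.000 |
| 5 | 14.5 < S ≤ 15 | 15 | 3.000 |
| 4 | 11.6 < S ≤ 12 | 12 | 3.000 |
| 3 | 8.7 < S ≤ 9 | 9 | 3.000 |
| 2 | 5.8 < S ≤ 6 | 6 | 3.000 |

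If means were rounded to one decimal first, which neither document says, 2.941 would become 2.9 and be moderate. Exactly 3.0 would still have no category.

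**Step 2: the two rules side by side, complete total score.**

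| Sum | Mean | Category (Protocol 9.2.2.1, SAP 2.1.7.5) | Counted in SAP 2.4.7.5 incidence |
|---|---|---|---|
| 49 | 2.882 | moderate | no |
| 50 | 2.941 | none | no |
| 51 | 3.000 | none | yes |
| 52 | 3.059 | high | yes |

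The two outputs conflict only at exactly 3.000. At 2.941 the only fault is the missing category.

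**Step 3: share at exactly 3.0, by assumption.** The documents give no DDS distribution. As an illustration, 400,000 patients were simulated with item = μ + 1.3 × (√ρ × f + √(1 − ρ) × e), rounded and limited to 1–6. Here f is a standard normal factor shared by a patient's items and e is independent standard normal. With μ from 1.5 to 3.0 the average item score was 1.79 to 3.03; ρ was 0.3 or 0.6.

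| Score | Share at exactly 3.0 | Times 15 patients |
|---|---|---|
| Total, 17 items | 0.5% to 3.2% | 0.08 to 0.48 |
| 5-item domains | 2.2% to 9.3% | 0.33 to 1.4 |
| 4-item domain | 2.9% to 11.2% | 0.44 to 1.7 |
| 3-item domain | 4.2% to 14.0% | 0.63 to 2.1 |

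This share is also the difference between counting with ≥3 and with >3. For example, at average item score 2.16 and ρ = 0.3, the 3-item domain gives 19.4% with ≥3 and 11.3% with >3, a difference of 8.1 points. For the total, the whole gap (2.941 and 3.000 together) holds 1.0% to 6.4%.

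**Step 4: size in this trial.** SAP section 2 reports 15 patients randomized. One patient at exactly 3.0 moves an overall incidence by 1/15 = 6.7 percentage points, and by more within one group or if fewer than 15 have a score.

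**The case against.** The strongest reply is that these are two outputs with two purposes. SAP 2.4.7.5 never calls its threshold high distress. Its cut is explicit and can be programmed without reference to the categories. That stands. A reader might infer that the report will carry two conflicting figures for high distress, or that the incidence depends on which line is programmed. The text does not establish either. Equating the two cuts is natural, since they apply to the same scores at the same number, but it remains an inference.

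The gap is also narrower than its wording suggests. From 2.9 to 3.0 looks like a range, but on every domain it is the single value 3.0. Only the total has a value strictly between, and one-decimal rounding would remove that one. This stands too, although no rounding rule is given and rounding does not help at 3.0.

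Third, little depends on it. The DDS is secondary and SAP 2.4.7 plans no p-values. The planned comparison is an ANCOVA on continuous change scores, in which no cut point enters. After early termination, SAP section 2 limits reporting to basic descriptive tables or listings. This settles the severity but not the defect, because counts and categories are just the kind of output that remains.

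What the reply does not answer is that the category rule, read on its own, fails to classify attainable scores in an output that the protocol lists.

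**Conclusion.** The point holds in a limited form. The category rule in Protocol 9.2.2.1 and SAP 2.1.7.5 is not exhaustive. At exactly 3.0 it is also out of step with the inclusive count in SAP 2.4.7.5. Both facts follow from the text and the item counts and need no assumption.

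The size does rest on assumptions: roughly 0.5 to 3% of totals and 2 to 14% of domain scores at exactly 3.0 under the correlated-item model above. Those figures are not estimates for this population. Among 15 patients they amount to less than half a patient on the total and about 0.3 to 2 on a domain, so quite possibly nobody is affected on a given score.

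A reader might also conclude that the inclusive cut is the correct one because it closes the gap. The documents do not settle that: both places that define high distress use the strict inequality. Severity is minor, a specification error worth correcting because the correction is almost free.

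**What to change.** Reconcile the inequality between SAP 2.1.7.5 and SAP 2.4.7.5 and state one contiguous rule for both outputs, including a label for means below 2.0. Say that it applies to unrounded means. For example, <2.0, ≥2.0 to <3.0, and ≥3.0 would be exhaustive and would match the SAP 2.4.7.5 count. The sponsor should first confirm the inequality against the cut-point publication cited in Protocol 9.2.2.1. If the SAP 2.4.7.5 count is meant to be the high-distress incidence, say so there; if not, say what it represents.

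If the agreed rule departs from Protocol 9.2.2.1, record that in SAP 1.5 or 1.6, which now declare no modifications. The cost is a few lines of SAP text and a check of the derivation program; no new data are needed.

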2.4.7.6 Investigator (clinician) reported outcome (ClinRO) endpoints

Overall Study Experience-sites (OSES) questionnaire

For OSES Part 1 (study-specific resource requirements), a descriptive summary will be provided for each approach group at each applicable visit, and a total time will be calculated for each patient and averaged within each approach group. Overall Study Experience-Sites Part 1 scores will be compared between approach groups using the same approach as the one used for primary endpoint (MMRM model) as described in [Section 2.4.4.1.1](#). This model will include fixed categorical effects of approach group, on randomization strata of screening HbA1c (<7.6%, $\geq 7.6\%$) and randomization strata of sites as well as continuous fixed covariates of corresponding baseline score.

For OSES Part 2 (relationship and satisfaction), a descriptive summary will be provided for each item for each approach group at Week 24. Item scores will be compared between approach groups using an ANOVA. This model will include fixed categorical effects of approach group, on randomization strata of screening HbA1c (<7.6%, $\geq 7.6\%$) and randomization strata of sites.

